10.4. Vital Signs

10.4.1. Vital Signs Variables

10.4.2. Analysis of Vital Signs

Values at each scheduled visit, change, and percentage change from baseline for vital signs, including systolic blood pressure, diastolic blood pressure, pulse, temperature, respiratory rate, and weight will be summarized descriptively for the SAF.

Normal ranges for vital sign values are defined in Table 9. For participants exhibiting vital sign abnormalities, the abnormal values will be listed along with their assigned treatment group. Alert vital signs are defined as an absolute value outside the defined normal range and percentage change greater than 25%. Note that the definition of alert vital signs does not apply for body temperature and weight. The abnormal values for participants exhibiting alert vital sign abnormalities will be listed.

Table 9: Normal Ranges for Vital Sign Values

Parameter	High Threshold	Low Threshold
Systolic blood pressure	≤ 155 mmHg	≥ 85 mmHg
Diastolic blood pressure	≤ 100 mmHg	≥ 40 mmHg
Pulse	≤ 100 bpm	≥ 45 bpm
Temperature	≤38°C	≥ 35.5°C
Respiratory rate	≤ 24 breaths/min	≥ 8 breaths/min

10.5. Physical Examination

Full physical examinations will be performed at screening and EOT, while limited physical examinations will be performed per individual status.

Full physical examinations should include vital signs, palpable tumor assessments, general appearance, skin, head, eyes, ears, nose, throat including Waldeyer lymphatic structures, lungs, breasts and axillae, cardiovascular system, back and spine, abdomen (including spleen size below the costal margin if applicable), extremities, infusion site, lymph nodes, and neurological examination.

Limited physical examinations will be guided by the individual participant's status and will include body systems associated with symptoms and/or the underlying DLBCL disease (eg, lymph node status, liver, spleen). Limited physical examinations may be focused on tumor response assessments (eg, lymph node status, liver, spleen) and AEs per INV discretion.

Disease involvement of the spleen/liver may be assessed as part of the full or limited physical examinations throughout the study and recorded data will be presented in a listing.

All physical examination results collected during the study will be listed by participant and body system.

10.6. Electrocardiograms

Twelve-lead ECGs including PR, RR, QT, QRS, QTcB, and QTcF intervals will be obtained for each participant during the study. Values at each scheduled visit, change, and percentage change from baseline will be summarized for each ECG parameter. Baseline will be determined as the latest of all nonmissing values before the first administration of tafasitamab or LEN.

Normal ranges for ECG values are defined in Table 10. Electrocardiogram values will also be considered abnormal if the absolute percentage change from baseline is more than 25% (30% for QRS interval). Participants exhibiting ECG abnormalities will be listed with study visit and assigned treatment group. Abnormal values for participants with alert ECG values, defined as both the absolute value and the percentage change from baseline being outside normal ranges, will be identified and listed. Outliers of QT, QTcB, and QTcF values, defined as absolute values > 450 milliseconds, > 500 milliseconds, or change from baseline > 30 milliseconds, will be summarized.

Table 10: Normal Ranges for Electrocardiogram Intervals

Parameter	High Threshold	Low Threshold
PR	≤ 220 ms	≥ 75 ms
RR	≤ 1330 ms	≥ 600 ms
QT	≤ 500 ms	≥ 300 ms
QRS	≤ 120 ms	≥ 50 ms
QTcB, QTcF	≤ 450 ms	≥ 295 ms
Heart rate	≤ 100 beats/min	≥ 45 beats/min

10.7. Analysis of B Symptoms and ECOG Status

The B symptoms and ECOG status of participants will be evaluated at each visit throughout the study. If any of the systemic symptoms (ie, weight loss, fever, or night sweats) are present, then B symptoms will be defined as present. Otherwise, B symptoms will be considered absent. For ECOG status, data will be categorized from 0 to 5.

Absolute and relative frequencies will be tabulated for B symptoms and ECOG status per visit using the SAF. Detailed information on B symptoms and ECOG status collected from the eCRF will be presented in participant data listings (based on the SAF).

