### 10.3 Statistical Analyses

A SAP detailing the statistical analyses will be finalized prior to first patient first visit. Details of the analyses to be performed on data from this study will be provided in a separate SAP. All analyses will be presented ( [REDACTED] ) and whenever applicable, overall.

Any deviations from the statistical analysis outlined in this protocol will be described, and reasons for the deviations listed, in the clinical study report.

Missing values will not be substituted by estimated values, but treated as missing in the statistical evaluation. All data from all patients dosed in the clinical study will be included in all listings, plots, summary tables, and statistical analyses where appropriate.

If a patient discontinues the study for reasons other than safety before the completion of the predefined safety observation window, this patient may be replaced.

In the event of a significant volume of missing data, sensitivity analyses for the efficacy [REDACTED] endpoints may be performed using the principle of multiple imputation.

This section is a summary of the planned statistical analyses of the most important endpoints including primary and secondary endpoints.

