6.1.4.2.1. Refractoriness to the Last Prior Antilymphoma Treatment Line

Refractoriness to the last prior treatment is defined as having less than a PR (ie, SD or PD) as the best overall response to the most recent therapy.

If the status for "refractoriness to the last prior treatment line" cannot be determined, the participant will be considered as having an "unknown" status.

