6.1.4.2.2. Rituximab Refractoriness

Rituximab refractoriness is defined as having reached less than a PR to any rituximab-containing treatment regimen. If the status for "rituximab refractoriness" cannot be determined, the participant will be considered as having an "unknown" status.

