9.2. Immunogenicity Analysis

Serum samples for the assessment of anti-tafasitamab antibodies will be collected as per the schedule of assessments detailed in Section 2 of the Protocol. In order to determine a participant's anti-tafasitamab antibody status, as a first step, a screening assay will be performed. Then, all screened positive samples will be tested again in a confirmatory assay. For all confirmed positive samples, the following additional assays will be performed: a semiquantitative ADA titer will be determined, the specificity toward MOR00208-hIgG1 or MOR00208-hIgG1/2a will be determined, and an nAb will be performed.

Anti-tafasitamab antibody samples will be defined as negative if they are screened or confirmed negative. Anti-tafasitamab antibody samples will be defined as positive if they are positive in

both the screening and the confirmatory assays. For all positive samples, an anti-tafasitamab antibody titer will be determined.

The immunogenicity data will be summarized for each treatment group and/or cohort and overall, using the IAS, as follows:

- Summary of the anti-tafasitamab antibody status; the number and percentage of participants will be tabulated to present the following categories:
 - Participants with pre-existing anti-tafasitamab antibodies (ie, participants who are positive for anti-tafasitamab antibodies on Cycle 1 Day 1).
 - Participants without anti-tafasitamab antibodies after treatment initiation (ie, participants who are negative for anti-tafasitamab antibodies on all occasions after Cycle 1 Day 1, irrespective of the baseline result).
 - Participants with anti-tafasitamab antibodies after treatment initiation (ie, participants who are positive for anti-tafasitamab antibodies on any occasion after Cycle 1 Day 1).
 - Participants with treatment-induced anti-tafasitamab antibodies (ie, participants who are negative for anti-tafasitamab antibodies on Cycle 1 Day 1 and positive on any other occasion).
 - Participants with treatment-boosted anti-tafasitamab antibodies (ie, participants who are positive for anti-tafasitamab antibodies on Cycle 1 Day 1 and who developed an increased titer on any other occasion).
- Summary of anti-tafasitamab antibody response per visit; the following will be tabulated:
 - Total number of participants
 - Number and percentage positive
 - Number and percentage negative
 - Number and percentage missing
- Summary of anti-tafasitamab antibody titer per visit; the following will be tabulated:

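### The SAP 10.7 rule for B symptoms has no missing category, so a partly blank record with no symptom marked present is classed as absent

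*SAP*

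**What the plan says.** SAP 10.7 derives one flag from three components. The first half of the rule is "If any of the systemic symptoms (ie, weight loss, fever, or night sweats) are present, then B symptoms will be defined as present". The second half is "Otherwise, B symptoms will be considered absent". No third category is given, and nothing is said about a component left blank or an assessment not done.

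The same section continues: "Absolute and relative frequencies will be tabulated for B symptoms and ECOG status per visit using the SAF". It does not say whether percentages use the whole SAF or only participants assessed at that visit. Appendix A lists the output as Table 3.6.2 on the SAF, and Listing 2.12.2 gives the participant-level B-symptom data.

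Protocol 10.3 sets the general rule: "Missing values will not be substituted by estimated values, but treated as missing in the statistical evaluation". SAP 10.7 neither repeats it nor sets it aside.

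Elsewhere the SAP does provide for undetermined values:
- SAP 6.1.4.2.1: where refractoriness to the last prior line "cannot be determined, the participant will be considered as having an" unknown status. SAP 6.1.4.2.2 (rituximab refractoriness) and 6.1.4.1 (early or late relapse) do the same.
- SAP 9.2: the per-visit antibody tables carry a row for "Number and percentage missing".

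SAP 10.7 also describes B symptoms as evaluated at every visit. The Protocol schedule of assessments (Table 3) plans them at screening, on Day 1 of the cycles and at end of treatment, but not at C1D4, C1D8 or the Day 15 visits.

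**The concern.** A two-way rule with a catch-all second branch puts every undetermined record in the favourable category. A participant with fever and weight loss marked no and night sweats left blank has an unknown status, yet the rule calls it absent. That amounts to substituting a value for a missing one, which Protocol 10.3 rules out.

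What is at stake is the accuracy of one by-visit safety table. The share of participants free of systemic symptoms could look higher than the data support, and a reader of the table could not tell how many of those counted as absent were confirmed absent. The mismatch over visits adds a second ambiguity: a programmer taking both sentences at face value could produce an absent result at a visit where no assessment was planned.

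**Working it through.** The documents state no prevalence, missing rate or expected count for B symptoms, so there is no figure to reproduce. The check has two parts.

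**1. Which records the rule reaches.** Suppose each of the three components can be yes, no or blank. The form itself is not shown, so this is an assumption. There are 3 × 3 × 3 = 27 patterns; 2 × 2 × 2 = 8 contain no yes, leaving 27 − 8 = 19 with at least one.

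| Record pattern | Patterns | SAP 10.7, read literally | With a missing category |
|---|---|---|---|
| At least one yes | 19 | present | present |
| All three no | 1 | absent | absent |
| No yes, one or two blank | 6 | absent | missing/incomplete |
| All three blank | 1 | absent, unless Protocol 10.3 is applied | missing/incomplete |

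These are patterns, not participants. The two rules agree wherever the status is known. They differ only where it is not, and there SAP 10.7 always moves the record to absent. No record is ever moved to present.

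**2. Direction and possible size.** At one visit let N be the participants tabulated, x those with at least one yes, and m those undetermined.
- Undetermined counted as absent: x/N.
- Undetermined left out: x/(N − m).
- Limits for the true prevalence among the N: x/N if none of the m has symptoms, (x + m)/N if all do.

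The literal rule therefore reports the lower limit as if it were the estimate.

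Inputs: N = 51 is the approximate planned enrolment (Protocol synopsis), assuming all are in the SAF and tabulated at the visit. Prevalence of 10% to 40% among those assessed and about 5% to 30% undetermined are assumptions with no source in the documents.

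| Assumed prevalence | m | x | x/N | x/(N − m) | Difference (points) | Limits |
|---|---|---|---|---|---|---|
| 10% | 3 | 5 | 5/51 = 9.8% | 5/48 = 10.4% | 0.6 | 9.8% to 15.7% |
| 20% | 5 | 9 | 9/51 = 17.6% | 9/46 = 19.6% | 1.9 | 17.6% to 27.5% |
| 40% | 15 | 14 | 14/51 = 27.5% | 14/36 = 38.9% | 11.4 | 27.5% to 56.9% |
| any | 0 | x | x/51 | x/51 | 0 | no gap |

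Differences are taken before rounding.

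The table treats the undetermined participants as having the same prevalence as the rest, which fits wholly missing assessments. For partly blank records the effect should usually be smaller, because a misclassification needs the blank component to be the participant's only positive one. For the same reason x/(N − m) is not exact either: a partly blank record with a yes is kept as present, while one without a yes drops out. That is why the count m should be shown beside the percentage.

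**The case against.** The strongest reply is that SAP 10.7 only explains how three recorded answers collapse into one flag and is silent on assessments not made. Protocol 10.3 then governs those, and SAP 4.1.7 bases by-visit summaries on the nominal visit in the eCRF, so an undone assessment supplies nothing to classify. ECOG status in the same section also has no missing row, and nobody would place a blank ECOG in grade 0. The shell for Table 3.6.2 is not available here: Appendix A keeps shells for non-standard tables in a separate document, and this table carries no standard mark, so a missing row and a denominator may be specified there. The SAP's unknown categories concern disease history, not scheduled visits. Finally, B symptoms are not among the primary or secondary endpoints in Table 1 of either document, no formal tests are planned (SAP 3.3), and the eCRF data are listed by participant.

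Most of this stands. A reader might infer that the SAP counts every missed assessment as symptom-free and so certainly understates prevalence. The documents do not support that, because Protocol 10.3 reasonably keeps a wholly missing assessment missing. A reader might also infer that the bias grows over time, is largest at end of treatment, or would look like improvement. Nothing in the documents shows a pattern of missingness, and B symptoms are a scheduled end-of-treatment assessment.

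The reply does not remove the partly blank record. There SAP 10.7 is not silent: its specific rule assigns the record to absent. The ECOG comparison does not help, since ECOG has no catch-all branch. The listings let a reader find incomplete records but do not correct the table.

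**Conclusion.** The concern holds in a limited form. Read literally, SAP 10.7 classes a partly completed record with no positive component as absent, does not expressly exempt an assessment recorded as not done, and leaves the denominator open. This conflicts with Protocol 10.3 and differs from the SAP's handling of undetermined values in 6.1.4 and 9.2.

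Taking the recorded components as correct, the error can only lower the prevalence in Table 3.6.2 or leave it unchanged. Its size cannot be stated from the documents: it is zero with complete records, and the 0.6 to 11.4 points above rest entirely on assumed prevalence and missing shares. It also depends on the form allowing blank components and on how the table is programmed. The table is descriptive and supports no endpoint, so this is a minor but easily removed defect.

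**What to change.** Replace the two-way rule in SAP 10.7 with a three-way one:
- *Present* if any component is recorded as present.
- *Absent* only if all three components are recorded as absent.
- *Missing/incomplete* in every other case, including an assessment not done.

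Add that Table 3.6.2 shows the number missing or incomplete at each visit, that percentages are based on participants with a determinable status, and that only visits where the schedule of assessments plans B symptoms are tabulated. Align the statement about every visit with that schedule. A reader can then compute the limits x/N and (x + m)/N from the table.

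The cost is a sentence or two in SAP 10.7, one row in Table 3.6.2 and a small programming change. No new data are needed.

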11. COVID-19 PANDEMIC-SPECIFIC ANALYSES

The following summaries will be created for both the primary and final analyses of the SAF.

- Number (%) of participants with positive test of COVID-19 during the treatment period.
- Number (%) of participants with positive test of COVID-19 during the study.
- Number (%) of participants with study treatment interruption/delay/discontinuation because of COVID-19.
- Number (%) of participants whose primary cause of death is COVID-19.
- Number (%) of participants with any TEAE due to COVID-19 by SOC and PT.
- Number (%) of participants with any serious TEAE by SOC and PT

The number (%) of participants with Protocol deviations related to COVID-19 will be summarized for the ENR. Listings of COVID-19 AEs and SAEs will be generated for the ENR.

[figure not shown]
12. CHANGES AND MODIFICATIONS TO THE ANALYSIS PLAN

All versions of the SAP are listed in Table 11.

Table 11: Statistical Analysis Plan Versions

SAP Version	Date
Original	18 JAN 2022
Amendment 1	24 OCT 2024

APPENDIX A. PLANNED TABLES, FIGURES, AND LISTINGS

This appendix provides a list of the planned tables, figures, and listings for the Clinical Study Report. Shells are provided in a separate document for tables that are not in the Standard Safety Tables v2.0.

The lists of tables, figures, and listings are to be used as guidelines. Modifications of the lists that do not otherwise affect the nature of the analysis will not warrant an amendment to the SAP.

Tables

Table No.	Title	Population	Standard
Baseline and	d Demographic Characteristics		
1.1.1	Analysis Sets	SPS	X
1.1.1.1	Screening Disposition	SPS	X
1.1.2.1	Summary of Participant Disposition	SPS	X
1.1.2.2	Summary of Participant Disposition by Cycle	ENR	X
1.1.3	Summary of Number of Participants Enrolled by Country and Site	ENR	X
1.1.4.1	Summary of Important Protocol Deviations	ENR	X
1.1.4.2	Summary of Protocol Deviations Related to COVID-19	ENR	X
1.1.5	Summary of Treatment Discontinuation Based on Components of Study Treatment	ENR	
1.1.5.1	Summary of Treatment Discontinuation of Both Tafasitamab and Lenalidomide Before Completing 12 Cycles	ENR	
1.1.5.2	Summary of Participants Who Discontinued Tafasitamab at Cycle 13 or Later	ENR	
1.1.6.x	Summary of Statistics of Enrollment	FAS (.1), SAF (.2)	
1.2.x	Summary of Demographics and Baseline Characteristics	ENR (.1), PAS (.2), SAF (.3), FAS (.4)	X
1.3.1.x	Summary of Baseline Disease Characteristics	PAS (.1), FAS (.2)	X
1.3.2.x	Summary of Bone Marrow Involvement at Screening	PAS (.1), FAS (.2)	
1.4.1.x	Summary of Preinfusion Medications for Tafasitamab	PAS (.1), FAS (.2)	X
1.4.2.x	Summary of Non-Antilymphoma Prior Medications	PAS (.1), FAS (.2)	X
1.4.3.x	Summary of Non-Antilymphoma Concomitant Medications	PAS (.1), FAS (.2)	X
1.4.4.x	Summary of Non-Antilymphoma Prior Nondrug Therapies	PAS (.1), FAS (.2)	
1.4.5.x	Summary of Non-Antilymphoma Concomitant Nondrug Therapies	PAS (.1), FAS (.2)	
1.4.6.x	Summary of Prior Lines of Antilymphoma Treatment	PAS (.1), FAS (.2)	
1.4.7.x	Summary of Nonstudy Antilymphoma Treatment	PAS (.1), FAS (.2)	
1.4.8	Summary of Nonstudy Antilymphoma Treatments: Drug Treatments	PAS	X
1.5.x	Summary of General Medical History and Current Medical Conditions	PAS (.1), FAS (.2)	X
Efficacy			•
2.1	Summary of Objective Response Rate by Investigator Assessment	FAS	
2.1.2	Sensitivity Analysis for Summary of Objective Response Rate by Investigator Assessment	PPS	
2.2.1	Summary of Progression-Free Survival by Investigator Assessment	FAS	

Table No.	Title	Population	Standard
2.2.1.1	Sensitivity Analysis for Summary of Progression-Free Survival by Investigator Assessment	PPS	
2.2.1.2	Sensitivity Analysis for Summary of Progression-Free Survival by Investigator Assessment - Change in Censoring	FAS	
2.2.2	Summary of Progression-Free Survival Follow-Up Time	FAS	
2.3	Summary of Duration of Response by Investigator Assessment	FAS	
2.3.1	Sensitivity Analysis for Summary of Duration of Response by Investigator Assessment	PPS	
2.3.2	Sensitivity Analysis for Summary of Duration of Response by Investigator Assessment - Change in Response Requirement	FAS	
Safety			
3.1.1.1	Summary of Exposure to Components of Study Treatment	ENR	
3.1.1.2.x	Summary of Exposure and Duration of Exposure to Tafasitamab	SAF (.1), PAS (.2), FAS (.3)	X
3.1.1.3.x	Summary of Exposure and Duration of Exposure to Lenalidomide	SAF (.1), PAS (.2), FAS (.3)	X
3.1.1.4.x	Summary of Exposure and Duration of Exposure to Study Treatment (Tafasitamab and Lenalidomide)	SAF (.1), PAS (.2), FAS (.3)	X
3.1.1.5.x	Summary of Exposure and Duration of Exposure to Study Drug (Tafasitamab or Lenalidomide)	SAF (.1), PAS (.2), FAS (.3)	X
3.1.1.6.x	Summary of Over-Infusion Rate of Tafasitamab	SAF (.1), PAS (.2), FAS (.3)	
			1
3.1.2.1.x	Summary of Dose Interruption of Tafasitamab	SAF (.1), PAS (.2), FAS (.3)	
3.1.2.2.x	Summary of Dose Reduction of Lenalidomide	SAF (.1), PAS (.2), FAS (.3)	
3.1.2.3.1.x	Summary of Skipped Doses of Tafasitamab	SAF (.1), PAS (.2), FAS (.3)	
3.1.2.3.2.x	Summary of Skipped Doses of Lenalidomide	SAF (.1), PAS (.2), FAS (.3)	
3.1.2.4	Summary of Study Treatment Interruption/Delay/Discontinuation Because of COVID-19	SAF	
3.1.3.1.x	Summary of Tafasitamab Compliance	SAF (.1), PAS (.2), FAS (.3)	X
3.1.3.2.x	Summary of Lenalidomide Compliance	SAF (.1), PAS (.2), FAS (.3)	X
3.2.1.x	Overall Summary of Treatment-Emergent Adverse Events	SAF (.1), PAS (.2), ENR (.3)	X
3.2.2.1.x	Summary of Treatment-Emergent Adverse Events by MedDRA System Organ Class and Preferred Term	SAF (.1), PAS (.2), ENR (.3)	X
3.2.2.2	Summary of COVID-19 Treatment-Emergent Adverse Events by MedDRA System Organ Class and Preferred Term	SAF	X
3.2.3.x	Summary of Treatment-Emergent Adverse Events by MedDRA Preferred Term in Decreasing Order of Frequency	SAF (.1), PAS (.2)	X
3.2.4.x	Summary of Treatment-Emergent Adverse Events by MedDRA System Organ Class, Preferred Term, and Maximum Severity	SAF (.1), PAS (.2)	X

Table No.	Title	Population	Standard
3.2.5.x	Summary of Treatment-Emergent Adverse Events by MedDRA System Organ Class, Preferred Term, and CTCAE Grade Category	SAF (.1), PAS (.2), ENR (.3)	X
3.2.6.x	Summary of Grade 3 or Higher Treatment-Emergent Adverse Events by MedDRA System Organ Class and Preferred Term	SAF (.1), PAS (.2), ENR (.3)	X
3.2.7.x	Summary of Grade 3 or Higher Treatment-Emergent Adverse Events by MedDRA Preferred Term in Decreasing Order of Frequency	SAF (.1), PAS (.2)	X
3.2.8.1.x	Summary of Serious Treatment-Emergent Adverse Events by MedDRA System Organ Class and Preferred Term	SAF (.1), PAS (.2), ENR (.3)	X
3.2.8.2.x	Summary of Serious Treatment-Emergent Adverse Events by MedDRA System Organ Class, Preferred Term, and CTCAE Grade Category	SAF (.1), PAS (.2), ENR (.3)	X
3.2.8.3	Summary of COVID-19 Serious Treatment-Emergent Adverse Events by MedDRA System Organ Class and Preferred Term	SAF	X
3.2.8.4.x	Summary of Grade 3 or Higher Serious Treatment-Emergent Adverse Events by MedDRA System Organ Class and Preferred Term	SAF (.1), PAS (.2), ENR (.3)	X
3.2.9.x	Summary of Serious Treatment-Emergent Adverse Events by MedDRA Preferred Term in Decreasing Order of Frequency	SAF (.1), PAS (.2)	X
3.2.10.1.x	Summary of Treatment-Related Treatment-Emergent Adverse Events by MedDRA System Organ Class and Preferred Term	SAF (.1), PAS (.2)	X
3.2.10.2.x	Summary of Tafasitamab-Related Treatment-Emergent Adverse Events by MedDRA System Organ Class and Preferred Term	SAF (.1), PAS (.2)	X
3.2.10.3.x	Summary of Lenalidomide-Related Treatment-Emergent Adverse Events by MedDRA System Organ Class and Preferred Term	SAF (.1), PAS (.2)	X
3.2.11.1.x	Summary of Treatment-Related Treatment-Emergent Adverse Events by MedDRA Preferred Term in Decreasing Order of Frequency	SAF (.1), PAS (.2)	X
3.2.11.2.x	Summary of Tafasitamab-Related Treatment-Emergent Adverse Events by MedDRA Preferred Term in Decreasing Order of Frequency	SAF (.1), PAS (.2)	X
3.2.11.3.x	Summary of Lenalidomide-Related Treatment-Emergent Adverse Events by MedDRA Preferred Term in Decreasing Order of Frequency	SAF (.1), PAS (.2)	X
3.2.13.1.x	Summary of Treatment-Related Treatment-Emergent Adverse Events by MedDRA System Organ Class, Preferred Term, and CTCAE Grade Category	SAF (.1), PAS (.2)	X
3.2.13.2.x	Summary of Tafasitamab-Related Treatment-Emergent Adverse Events by MedDRA System Organ Class, Preferred Term, and CTCAE Grade Category	SAF (.1), PAS (.2)	X
3.2.13.3.x	Summary of Lenalidomide-Related Treatment-Emergent Adverse Events by MedDRA System Organ Class, Preferred Term, and CTCAE Grade Category	SAF (.1), PAS (.2)	X
3.2.14.1.x	Summary of Grade 3 or Higher Treatment-Related Treatment-Emergent Adverse Events by MedDRA System Organ Class and Preferred Term	SAF (.1), PAS (.2)	X
3.2.14.2.x	Summary of Grade 3 or Higher Tafasitamab-Related Treatment-Emergent Adverse Events by MedDRA System Organ Class and Preferred Term	SAF (.1), PAS (.2)	X

Table No.	Title	Population	Standard
3.2.14.2.x	Summary of Grade 3 or Higher Lenalidomide-Related Treatment-Emergent Adverse Events by MedDRA System Organ Class and Preferred Term	SAF (.1), PAS (.2)	X
3.2.15.x	Summary of Treatment-Related Serious Treatment-Emergent Adverse Events by MedDRA System Organ Class and Preferred Term	SAF (.1), PAS (.2)	X
3.2.16	Summary of Treatment-Emergent Adverse Events With a Fatal Outcome by MedDRA System Organ Class and Preferred Term	SAF (.1), PAS (.2)	X
3.2.19.1.1.x	Summary of Treatment-Emergent Adverse Events Leading to Tafasitamab Infusion Interruption by MedDRA System Organ Class and Preferred Term	SAF (.1), PAS (.2)	X
3.2.19.1.2.x	Summary of Treatment-Emergent Adverse Events Leading to Tafasitamab Infusion Interruption by MedDRA System Organ Class, Preferred Term, and CTCAE Grade Category	SAF (.1), PAS (.2)	X
3.2.19.1.3.x	Summary of Treatment-Emergent Adverse Events Leading to Skipped Tafasitamab Infusion by MedDRA System Organ Class and Preferred Term	SAF (.1), PAS (.2)	X
3.2.19.1.4.x	Summary of Treatment-Emergent Adverse Events Leading to Skipped Tafasitamab Infusion by MedDRA System Organ Class, Preferred Term, and CTCAE Grade Category	SAF (.1), PAS (.2)	X
3.2.19.2.1.x	Summary of Treatment-Emergent Adverse Events Leading to Skipped Lenalidomide Dose by MedDRA System Organ Class and Preferred Term	SAF (.1), PAS (.2)	X
3.2.19.2.2.x	Summary of Treatment-Emergent Adverse Events Leading to Skipped Lenalidomide Dose by MedDRA System Organ Class, Preferred Term, and CTCAE Grade Category	SAF (.1), PAS (.2)	X
3.2.19.2.3.x	Summary of Treatment-Emergent Adverse Events Leading to Lenalidomide Dose Reduction by MedDRA System Organ Class and Preferred Term	SAF (.1), PAS (.2)	X
3.2.19.2.4.x	Summary of Treatment-Emergent Adverse Events Leading to Lenalidomide Dose Reduction by MedDRA System Organ Class, Preferred Term, and CTCAE Grade Category	SAF (.1), PAS (.2)	X
3.2.20.1.x	Summary of Treatment-Emergent Adverse Events Leading to Discontinuation of Tafasitamab by MedDRA System Organ Class and Preferred Term	SAF (.1), PAS (.2)	X
3.2.20.2.x	Summary of Treatment-Emergent Adverse Events Leading to Discontinuation of Lenalidomide by MedDRA System Organ Class and Preferred Term	SAF (.1), PAS (.2)	X
3.2.24.1.x	Summary of Deaths	SAF (.1), PAS (.2), ENR (.3)	X
3.2.24.2	Summary of Deaths Caused by COVID-19	ENR	X
3.2.25.x	Summary of Treatment-Emergent Adverse Events by MedDRA System Organ Class, Preferred Term, and Highest Intensity	SAF (.1), PAS (.2), ENR (.3)	X
3.2.26.x	Summary of Infusion-Related Treatment-Emergent Adverse Events by MedDRA System Organ Class and Preferred Term	SAF (.1), PAS (.2)	X
3.2.27.x	Summary of Infusion-Related Treatment-Emergent Adverse Events by MedDRA System Organ Class, Preferred Term, and CTCAE Grade Category	SAF (.1), PAS (.2)	X

Table No.	Title	Population	Standard
3.2.28.x	Summary of Grade 3 or Higher Infusion-Related Treatment-Emergent Adverse Events by MedDRA System Organ Class and Preferred Term	SAF (.1), PAS (.2)	X
3.2.29.x	Summary of Treatment-Emergent Adverse Events of Special Interest by MedDRA System Organ Class and Preferred Term	SAF (.1), PAS (.2), ENR (.3)	X
3.2.30.x	Summary of Treatment-Emergent Adverse Events of Special Interest by MedDRA System Organ Class, Preferred Term, and CTCAE Grade Category	SAF (.1), PAS (.2), ENR (.3)	X
3.2.31.x	Summary of Grade 3 or Higher Treatment-Emergent Adverse Events of Special Interest by MedDRA System Organ Class and Preferred Term	SAF (.1), PAS (.2), ENR (.3)	X
3.2.32.x	Summary of Treatment-Emergent Adverse Events by MedDRA System Organ Class, Preferred Term, and Outcome	SAF (.1), PAS (.2)	
3.2.33.x	Summary of Treatment-Emergent Adverse Events by MedDRA System Organ Class, Preferred Term, and Action Taken With Tafasitamab	SAF (.1), PAS (.2)	
3.2.34.x	Summary of Treatment-Emergent Adverse Events by MedDRA System Organ Class, Preferred Term, and Action Taken With Lenalidomide	SAF (.1), PAS (.2)	X
3.2.35.1.x	Summary of Time to Onset of Neutropenia Since Cycle 1 Day 1	SAF (.1), PAS (.2)	
3.2.35.2.x	Summary of Time to Onset of Febrile Neutropenia Since Cycle 1 Day 1	SAF (.1), PAS (.2)	
3.2.36.1.x	Summary of Time to Onset of Neutropenia Since First Dose of Tafasitamab	SAF (.1), PAS (.2)	
3.2.36.2.x	Summary of Time to Onset of Febrile Neutropenia Since First Dose of Tafasitamab	SAF (.1), PAS (.2)	
3.3.1.1	Summary of Laboratory Values - Hematology	SAF	X
3.3.1.2	Summary of Laboratory Values - Chemistry	SAF	X
3.3.1.3	Summary of Laboratory Values - Coagulation	SAF	X
3.3.1.4	Summary of Laboratory Values - Liver Biochemistry	SAF	X
3.3.2.1	Shift Summary of Hematology Values - to the Worst Abnormal Value	SAF	X
3.3.2.2	Shift Summary of Chemistry Values - to the Worst Abnormal Value	SAF	X
3.3.2.3	Shift Summary of Coagulation Values - to the Worst Abnormal Value	SAF	X
3.3.2.4	Shift Summary of Liver Biochemistry Values - to the Worst Abnormal Value	SAF	X
3.3.3.1	Shift Summary of Hematology Laboratory Values in CTCAE Grade - to the Worst Abnormal Value	SAF	X
3.3.3.2	Shift Summary of Chemistry Laboratory Values in CTCAE Grade - to the Worst Abnormal Value	SAF	X
3.3.3.3	Shift Summary of Coagulation Laboratory Values in CTCAE Grade - to the Worst Abnormal Value	SAF	X
3.3.3.4	Shift Summary of Liver Biochemistry Laboratory Values in CTCAE Grade - to the Worst Abnormal Value	SAF	X
3.3.4.1	Treatment-Emergent Worsening of Laboratory Abnormalities - Hematology	SAF	X

Table No.	Title	Population	Standard
3.3.4.2	Treatment-Emergent Worsening of Laboratory Abnormalities - Chemistry	SAF	X
3.3.4.3	Treatment-Emergent Worsening of Laboratory Abnormalities - Coagulation	SAF	X
3.3.4.4	Treatment-Emergent Worsening of Laboratory Abnormalities - Liver Biochemistry	SAF	X
3.4.1	Summary of Systolic Blood Pressure	SAF	X
3.4.2	Summary of Diastolic Blood Pressure	SAF	X
3.4.3	Summary of Pulse	SAF	X
3.4.4	Summary of Respiratory Rate	SAF	X
3.4.5	Summary of Body Temperature	SAF	X
3.4.6	Summary of Body Weight	SAF	X
3.5.1	Summary of PR Interval (ms) From 12-Lead ECG	SAF	X
3.5.2	Summary of QRS Interval (ms) From 12-Lead ECG	SAF	X
3.5.3	Summary of QT Interval (ms) From 12-Lead ECG	SAF	X
3.5.4	Summary of QTcB Interval (ms) From 12-Lead ECG	SAF	X
3.5.5	Summary of QTcF Interval (ms) From 12-Lead ECG	SAF	X
3.5.6	Summary of RR Interval (ms) From 12-Lead ECG	SAF	X
3.5.7	Summary of Heart Rate (beats/min) From 12-Lead ECG	SAF	X
3.5.8	Summary of Outliers of QT, QTcB, and QTcF Interval Values (ms) From 12-Lead ECG	SAF	X
3.6.1	Summary of ECOG Status by Visit	SAF	
3.6.2	Summary of B Symptoms by Visit	SAF	
3.2.7.1	Summary of Positive COVID-19 Test During Study Treatment	SAF	
3.2.7.2	Summary of Positive COVID-19 Test (Any Time)	SAF	

Note: Tables ending with ".x" will use the number indicated in the population.

Figures

Figure No.	Title	
4.4.1.1	Swimmer Plot of Disease Response Assessments for Participants in the FAS	
4.4.1.2	Swimmer Plot of Disease Response Assessments for Participants in the PPS	
4.4.2	Kaplan-Meier Estimates of Progression-Free Survival	
4.5.1.1	Participants in the SAF With Treatment-Emergent Adverse Events by MedDRA Preferred Term and CTCAE Grade Category	
4.5.1.2	Participants in the PAS With Treatment-Emergent Adverse Events by MedDRA Preferred Term and CTCAE Grade Category	
4.5.2.1	Participants in the SAF With Hematologic Treatment-Emergent Adverse Events by MedDRA Preferred Term, and CTCAE Grade Category	
4.5.2.2	Participants in the PAS With Hematologic Treatment-Emergent Adverse Events by MedDRA Preferred Term and CTCAE Grade Category	
4.5.3.1	Participants in the SAF With Nonhematologic Treatment-Emergent Adverse Events by MedDRA Preferred Term and CTCAE Grade Category	
4.5.3.2	Participants in the PAS With Nonhematologic Treatment-Emergent Adverse Events by MedDRA Preferred Term and CTCAE Grade Category	
6.3.1.1	Box Plot of Absolute Neutrophil Count	
6.3.2.1	Box Plot of Platelet Count	
6.3.3.1	Box Plot of Hemoglobin	

Listings

Listing No. Title 2.1.1 Participant Disposition 2.2.1 Inclusion/Exclusion Criteria Violations 2.2.2 Protocol Deviations 2.3.1 Analysis Population 2.4.1 Demographics and Baseline Characteristics 2.4.2 Baseline Disease Characteristics 2.4.3 Medical History 2.4.4 Non-Antilymphoma Prior and Concomitant Medications 2.4.5 Non-Antilymphoma Prior and Concomitant Nondrug Therapies 2.4.6 Prior Antilymphoma Drug Treatment 2.4.7 Prior Antilymphoma Radiotherapy Treatment 2.4.8 Prior Antilymphoma Surgeries/Procedures 2.4.9 Nonstudy Antilymphoma Treatment - Drug Treatment 2.4.10 Nonstudy Antilymphoma Treatment - Radiotherapy Treatment
2.2.1 Inclusion/Exclusion Criteria Violations 2.2.2 Protocol Deviations 2.3.1 Analysis Population 2.4.1 Demographics and Baseline Characteristics 2.4.2 Baseline Disease Characteristics 2.4.3 Medical History 2.4.4 Non-Antilymphoma Prior and Concomitant Medications 2.4.5 Non-Antilymphoma Prior and Concomitant Nondrug Therapies 2.4.6 Prior Antilymphoma Drug Treatment 2.4.7 Prior Antilymphoma Radiotherapy Treatment 2.4.8 Prior Antilymphoma Surgeries/Procedures 2.4.9 Nonstudy Antilymphoma Treatment - Drug Treatment
2.2.2 Protocol Deviations 2.3.1 Analysis Population 2.4.1 Demographics and Baseline Characteristics 2.4.2 Baseline Disease Characteristics 2.4.3 Medical History 2.4.4 Non-Antilymphoma Prior and Concomitant Medications 2.4.5 Non-Antilymphoma Prior and Concomitant Nondrug Therapies 2.4.6 Prior Antilymphoma Drug Treatment 2.4.7 Prior Antilymphoma Radiotherapy Treatment 2.4.8 Prior Antilymphoma Surgeries/Procedures 2.4.9 Nonstudy Antilymphoma Treatment - Drug Treatment
2.3.1 Analysis Population 2.4.1 Demographics and Baseline Characteristics 2.4.2 Baseline Disease Characteristics 2.4.3 Medical History 2.4.4 Non-Antilymphoma Prior and Concomitant Medications 2.4.5 Non-Antilymphoma Prior and Concomitant Nondrug Therapies 2.4.6 Prior Antilymphoma Drug Treatment 2.4.7 Prior Antilymphoma Radiotherapy Treatment 2.4.8 Prior Antilymphoma Surgeries/Procedures 2.4.9 Nonstudy Antilymphoma Treatment - Drug Treatment
2.4.1 Demographics and Baseline Characteristics 2.4.2 Baseline Disease Characteristics 2.4.3 Medical History 2.4.4 Non-Antilymphoma Prior and Concomitant Medications 2.4.5 Non-Antilymphoma Prior and Concomitant Nondrug Therapies 2.4.6 Prior Antilymphoma Drug Treatment 2.4.7 Prior Antilymphoma Radiotherapy Treatment 2.4.8 Prior Antilymphoma Surgeries/Procedures 2.4.9 Nonstudy Antilymphoma Treatment - Drug Treatment
2.4.2 Baseline Disease Characteristics 2.4.3 Medical History 2.4.4 Non-Antilymphoma Prior and Concomitant Medications 2.4.5 Non-Antilymphoma Prior and Concomitant Nondrug Therapies 2.4.6 Prior Antilymphoma Drug Treatment 2.4.7 Prior Antilymphoma Radiotherapy Treatment 2.4.8 Prior Antilymphoma Surgeries/Procedures 2.4.9 Nonstudy Antilymphoma Treatment - Drug Treatment
2.4.3 Medical History 2.4.4 Non-Antilymphoma Prior and Concomitant Medications 2.4.5 Non-Antilymphoma Prior and Concomitant Nondrug Therapies 2.4.6 Prior Antilymphoma Drug Treatment 2.4.7 Prior Antilymphoma Radiotherapy Treatment 2.4.8 Prior Antilymphoma Surgeries/Procedures 2.4.9 Nonstudy Antilymphoma Treatment - Drug Treatment
2.4.4 Non-Antilymphoma Prior and Concomitant Medications 2.4.5 Non-Antilymphoma Prior and Concomitant Nondrug Therapies 2.4.6 Prior Antilymphoma Drug Treatment 2.4.7 Prior Antilymphoma Radiotherapy Treatment 2.4.8 Prior Antilymphoma Surgeries/Procedures 2.4.9 Nonstudy Antilymphoma Treatment - Drug Treatment
2.4.5 Non-Antilymphoma Prior and Concomitant Nondrug Therapies 2.4.6 Prior Antilymphoma Drug Treatment 2.4.7 Prior Antilymphoma Radiotherapy Treatment 2.4.8 Prior Antilymphoma Surgeries/Procedures 2.4.9 Nonstudy Antilymphoma Treatment - Drug Treatment
2.4.6 Prior Antilymphoma Drug Treatment 2.4.7 Prior Antilymphoma Radiotherapy Treatment 2.4.8 Prior Antilymphoma Surgeries/Procedures 2.4.9 Nonstudy Antilymphoma Treatment - Drug Treatment
2.4.7 Prior Antilymphoma Radiotherapy Treatment 2.4.8 Prior Antilymphoma Surgeries/Procedures 2.4.9 Nonstudy Antilymphoma Treatment - Drug Treatment
2.4.8 Prior Antilymphoma Surgeries/Procedures 2.4.9 Nonstudy Antilymphoma Treatment - Drug Treatment
